7.3 Statistical Methods

We will utilize standard measures to report outcomes and measure differences between groups. Specifically, we will use descriptive statistics, including mean (standard deviation) and median (interquartile range). Normality will be assessed using histograms and the Kolmogorov–Smirnov test. Categorical variables will be compared using the chi-squared test or Fisher exact test. Continuous variables will be compared using the independent samples t or Mann–Whitney U test.

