3.1 General Design

This is a small scale pilot study to evaluate if core warming improves respiratory physiology of mechanically ventilated patients with COVID-19, allowing earlier weaning from ventilation, and greater overall survival. This prospective, randomized study will include 22 patients diagnosed with COVID-19, and undergoing mechanical ventilation for the treatment of respiratory failure. Patients will be randomized in a 1:1 fashion with 11 patients (Group A) randomized to undergo core warming, and the other 11 patients (Group B) serving as the control group who will not have the ensoETM device used. Patients randomized to Group A will have core warming initiated in the ICU or other clinical environment in which they are being treated after enrollment and provision of informed consent from appropriate surrogate or legally authorized representative.

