6.5.1 Data Collection and Follow-up for Withdrawn Subjects

We will attempt to have one final visit or contact to follow up regarding adverse events for participants who withdraw prior to the 30 day follow up visit. During this contact they will be asked for permission to have the study team look into their survival status via their electronic medical records and publicly available means.

7 Statistical Plan

Primary Endpoint

The primary endpoint of this study will be the change in PaO₂/FiO₂ ratio at 0, 24, 48, and 72 hours after implementation of core warming of ventilated patients. This endpoint will be compared between patients receiving core warming and those randomized to undergo standard care (standard temperature management, with or without antipyretics as needed).

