7.2 Sample Size and Power Determination

Based on a prior study in patients with sepsis, a maximum temperature of 38.3°C to 39.4°C was associated with survival (aHR 0.61 [95% CI, 0.39-0.99]).[29] However, the effect of warming specific to COVID-19 patients remains uncertain, and as such, we are unable to accurately perform a power calculation for this pilot study. We believe that a total of 10 patients for each group will be required to yield the necessary pilot data to make an appropriate conclusion regarding the potential utility of core warming in reducing viral shedding, improving pulmonary physiology, reducing mechanical ventilation duration, and increasing patient survival. It is anticipated that data from this pilot study can be used for planning future larger studies.

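### The primary P/F comparison is an unadjusted t or Mann–Whitney test picked after a normality check with no stated form, level or rule; one baseline-adjusted analysis should be fixed in advance

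*Combined protocol and SAP*

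**What the plan says.** Section 7.3 has two relevant sentences. The first says "Normality will be assessed using histograms" and a KS test; the second says "Continuous variables will be compared using the independent samples t or Mann–Whitney U test". It does not state the significance level of the KS test, whether its critical value is corrected for an estimated mean and SD (Lilliefors), or whether normality is judged per arm or pooled. It also does not say how histogram and test are combined, or which finding leads to which comparison. Section 7.3.1, headed Efficacy Analysis, names no method. No baseline-adjusted analysis appears anywhere.

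The outcome that matters most here is set at the start of Section 7: "The primary endpoint of this study will be the change in PaO₂/FiO₂ ratio at 0, 24, 48, and 72 hours". Section 3.2 describes the purpose in terms of P/F at 72 hours, while Section 3.2.1 lists all four time points. Section 3.1 sets the size: "Patients will be randomized in a 1:1 fashion with 11 patients (Group A) randomized to undergo core warming", with 11 controls. Section 7.2 instead gives 10 per group and says "we are unable to accurately perform a power calculation for this pilot study". Sections 5.2 and 8.6 state that the physicians and the study team know the assignment.

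**The concern.** There are two separate weaknesses.

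The first is that the primary test is not fixed before the data are seen. It follows from a look at about 11 values per arm, by people who know the allocation, with no written criterion. Two analysts could follow Section 7.3 faithfully and report different tests for the same outcome.

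The second does not depend on the normality check. Both candidate tests are unadjusted. A change score subtracts the baseline in full, however weakly baseline predicts the 72-hour value. When the correlation is moderate, this adds noise that a covariate would remove. In a 22-patient pilot meant to inform larger studies, what is at stake is the precision and credibility of the effect estimate.

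**Working it through.** The plan states no power, effect size or SD, so there is no figure of its own to reproduce. Every distribution below is an assumption, shown as a range.

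**Step 1. How often would KS reject normality in one arm?** Inputs: n = 11 (Section 3.1); mean and SD estimated from the sample; normality level 0.05 (assumed). Critical values at n = 11 are 0.391 uncorrected and 0.252 Lilliefors (simulated). Each KS figure uses 20,000 simulated samples.

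| Assumed shape | Uncorrected KS | Lilliefors KS |
|---|---|---|
| Normal | 0.0% | 4.7% |
| Lognormal, log-SD 0.4 | 0.1% | 14% |
| Lognormal, log-SD 0.5 | 0.2% | 20% |
| Lognormal, log-SD 0.8 | 1.7% | 38% |
| Lognormal, log-SD 1.0 | 3.7% | 51% |
| Gamma, shape 2 | 0.1% | 18% |
| Exponential | 0.6% | 33% |
| Ventilator days (lognormal, median 12, log-SD 0.8, capped at 30) | 0.04% | 17% |

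Other readings of the text, for the skewed shapes:
- Rejection in at least one arm: 0.1–7.8% uncorrected, 27–76% Lilliefors.
- All 22 pooled: 0.6–24% and 27–83%.
- 10 per arm (Section 7.2): 0.01–2.8% and 13–46%.

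**Step 2. What does selecting the test this way do to error and power?** At 11 per arm and two-sided 0.05, the procedure that switches to Mann–Whitney when either arm rejects has type I error of 4.0–5.2% (uncorrected) and 5.1–5.5% (Lilliefors). Power for a two-fold ratio, always t against always Mann–Whitney:
- lognormal log-SD 0.5: 82% and 85%
- lognormal log-SD 0.8: 38% and 46%
- lognormal log-SD 1.0: 22% and 32%
- exponential: 27% and 26%
- gamma: 53% and 50%
- capped ventilator days, median halved: 45% and 45%

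**Step 3. Does t or Mann–Whitney matter for P/F change?** Assume lognormal P/F with median 150, log-SD 0.45, effect 0.4 log units (ratio e^0.4 ≈ 1.49) and 11 per arm. Power on raw change, t and Mann–Whitney, is 40.5% and 39.9% (baseline correlation ρ = 0.3), 51.3% and 51.5% (0.5), and 71.3% and 71.8% (0.7). The two are practically equal.

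**Step 4. What does baseline adjustment add?** On the log scale, with √(2/11) = 0.4264:

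- SE of ANCOVA ≈ 0.45 × √(1 − ρ²) × 0.4264
- SE of log change = 0.45 × √(2(1 − ρ)) × 0.4264
- variance ratio = (1 − ρ²) / (2(1 − ρ)) = (1 + ρ)/2

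| ρ | SE, ANCOVA | 0.4/SE | SE, log change | 0.4/SE | Variance ratio |
|---|---|---|---|---|---|
| 0.3 | 0.183 | 2.19 | 0.227 | 1.76 | 0.65 |
| 0.5 | 0.166 | 2.41 | 0.192 | 2.09 | 0.75 |
| 0.7 | 0.137 | 2.92 | 0.149 | 2.69 | 0.85 |

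The non-central t distribution turns these into power of 55%, 63% and 79% for ANCOVA (19 df) and 39%, 51% and 73% for log change (20 df). The ANCOVA formula ignores chance baseline imbalance, so it is slightly optimistic.

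Simulated power, log ANCOVA against t on raw change:

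| ρ | Log ANCOVA | t, raw change | Gain | Gain without the log |
|---|---|---|---|---|
| 0.3 | 53% | 40% | 13 points | about 8 |
| 0.5 | 61% | 52% | 9 points | about 4 |
| 0.7 | 78% | 73% | 5 points | about −1 |

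Type I error of the log ANCOVA was 4.6–5.6%.

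**The case against.** A reader might infer that the KS test almost never rejects, so that the check does nothing and skewed outcomes are sent to a t-test. The documents do not support this. Near-zero rejection holds only for the uncorrected form, which Section 7.3 does not specify; the Lilliefors form rejects 14–51% per arm. Histograms are named alongside KS, so an analyst could choose Mann–Whitney for ventilation duration by eye. No sentence makes t the default.

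It is also tempting to say that the plan throws away the baseline P/F. It does not: a change score uses baseline, only with a fixed coefficient of one.

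The strongest defence is that the consequences of the test choice are small. Type I error stays near 5%, and t and Mann–Whitney have nearly equal power for P/F change. The advantage of Mann–Whitney reaches about 10 points only for the most skewed shape tried, and gamma or exponential data slightly favour t. All of this stands. So does the remark that the ANCOVA gain says nothing about the normality check, because Mann–Whitney is equally unadjusted. The gain comes from two other changes (covariate and log), on data simulated as lognormal. A pilot of 22 also lowers the stakes.

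What the defence does not answer is that no primary test is fixed, and that a more efficient analysis is available from data already collected.

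**Conclusion.** The point holds in this form: the choice of test is data-dependent with no stated rule, the check is weak at 11 per arm under either version of KS, and the primary comparison is unadjusted. It is worth correcting, but it does not invalidate the trial. The normality check costs little in type I error (about 4.0–5.5%). Its harm is an unfixed primary test in unblinded hands.

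The missing adjustment costs about 5–13 points of power, provided that P/F is roughly lognormal with log-SD 0.45, the effect is 0.4 log units and the baseline correlation is 0.3–0.7. None of these values is in the documents. The gain shrinks as the correlation rises, and at 0.7 it depends wholly on working on the log scale. That the test is unfixed and unadjusted rests on the text alone; the size of the gain rests on the assumptions.

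**What to change.** In Section 7.3, remove the normality check as a selector and keep histograms as description. Pre-specify the primary analysis as ANCOVA of log P/F at 72 h on arm and log 0-hour P/F, reported as a ratio with a 95% CI. Analyse 24 h and 48 h the same way, as supportive.

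For ventilation duration, name one fixed rank-based test. State where deaths and patients still ventilated at day 30 are ranked. Fix the day-30 anchor too, since Section 3.1.3 counts from the start of treatment and Section 6.2.3 from study completion.

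The cost is a few sentences and no new data. Three things should be accepted openly:
- Making 72 h primary is an endpoint decision. Section 3.2 supports it, but Sections 3.2.1 and 7 list four time points and must be brought into line.
- The effect becomes a ratio rather than an absolute difference, and one degree of freedom is spent.
- ANCOVA does not settle what happens when a patient has no 72-hour P/F because of death or extubation. That needs its own rule, particularly as Section 7.4 analyses only patients who completed.

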7.3.1 Efficacy Analysis

This is a pilot study to determine the potential role of core warming during COVID-19 treatment..

7.3.2 Interim Safety Analysis

All subjects entered into the study and randomized at the baseline timepoint will have detailed information collected on adverse events for the overall study safety analysis. An interim safety analysis will be performed after the first 10 subjects are enrolled in the trial. At this time the safety and tolerability of the study device will be assessed and if deemed safe and appropriate, enrollment will continue to 22 subjects.

7.4 Subject Population(s) for Analysis

All patients enrolled, randomized to a study arm, and completed in the study will be included for analysis.

8 Safety and Adverse Events

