4.3 Subject Recruitment

Subjects will be recruited from the ICU or other clinical environment in which they are being treated (Emergency Department, step-down unit, etc.). Patients will be identified by the PI or other study investigators/coordinators as available. All patients without a DNR order with a diagnosis of COVID-19 and meeting inclusion criteria will be eligible for screening for any exclusion criteria. The study team will pre-screen the potential subject's EMR, to assess all other inclusion/exclusion criteria, prior to approaching the patient and/or their surrogate / legally authorized representative about study participation. Written informed consent for the research study will be obtained from patient's surrogate or legally authorized representative prior to enrollment. If a patient enrolled in the study gains the capacity to consent for him/herself while the study is in progress, the patient will be approached by a study team member and the consent document will be presented directly to the patient. All questions the patient might have will be answered. The patient will be given the opportunity to either withdraw from the study or sign the consent form. The patient will be informed that his or her decision to withdraw from the study will not affect his or her medical care

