4.4 Duration of Study Participation

Participants will be involved for approximately 30 days, including screening, treatment, and follow-up. After consent, patient participation in the intervention phase will last 72 hours for active treatment. The follow up for determination of outcome and duration of mechanical ventilation will occur at 1-month post-treatment. Additional data will be collected via chart review.

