4.5 Total Number of Subjects and Sites

Recruitment will end when 22 participants are randomized.

5 Study Intervention

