5.1 Intervention Regimen

Patients who are randomized to core warming will have the esophageal heat transfer device placed in the ICU or other treatment area where patient is undergoing mechanical ventilation. The device will remain in place until the study is completed (72 hours). The device will be set to 42°C for the duration of the study period, with the exception of any elevations in patient temperature as described in section 3 above.

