5.2 Blinding

Due to the nature of this study, the physicians will not be blinded to the randomization assignment, however participants will be blinded. Once a subject is randomized, the research team will receive the randomization assignment (core warming or standard of care) and proceed with the procedures per the assignment.

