6.2.3 Post treatment

Participant's clinical status and outcome will be reviewed 30 days after study completion.

The following procedures will be collected:

- Interim medical history review /concomitant medications
- Physical Exam & Vital Signs
- Adverse Event/Unanticipated Problem assessment and recording

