6.5 Subject Withdrawal

Subjects may withdraw from the study at any time without impact to their care. They may also be discontinued from the study at the discretion of the Investigator for lack of adherence to study procedures or visit schedules, AEs, or should it become clinically necessary to deviate from the study protocol during the course of the study. The Investigator may also withdraw subjects who violate the study plan, or to protect the subject for reasons of safety or for administrative reasons. It will be documented whether or not each subject completes the clinical study. We will attempt to have one final visit or contact to follow up regarding adverse events for participants who withdraw prior to the 30 day follow up visit.

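### Section 7.4 analyses only randomised patients who 'completed', an undefined post-randomisation condition that can bias every efficacy comparison in either direction

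*Combined protocol and SAP*

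**What the plan says.** Section 7.4 is one sentence: "All patients enrolled, randomized to a study arm, and completed in the study will be included for analysis". It is the only analysis-population statement; no intention-to-treat or other all-randomised efficacy set appears elsewhere.

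Several other sections determine who fails to complete:

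- **6.5** allows withdrawal at any time and adds: "They may also be discontinued from the study at the discretion of the Investigator for lack of adherence to study procedures or visit schedules". Adverse events and clinically necessary deviations are further grounds. Completion status is to be documented, but no criterion is given.
- **5.2** states that "the physicians will not be blinded to the randomization assignment"; 8.6 says the same of the study team.
- **4.3** covers patients who regain capacity: "The patient will be given the opportunity to either withdraw from the study or sign the consent form".
- **4.5** closes enrolment by number randomised: "Recruitment will end when 22 participants are randomized". Losses are not replaced.

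Two sections look past completion, but neither repairs 7.4. Section 7.3.2 covers all randomised patients for adverse events only. Section 6.5.1 seeks survival status for withdrawn patients, with permission, but does not say that it enters the analysis.

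**The concern.** Randomisation makes the two groups of 11 comparable on the day they are formed. A rule that keeps only completers replaces them with groups shaped by what happened afterwards, and here staff who know the assignment can influence that.

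The grounds for discontinuation apply to both arms, but adverse events or non-adherence tied to the device can arise only under warming. Those patients may be doing worse, which would flatter warming. Patients who recover capacity and then decline to continue may be doing better, which pulls the other way. The direction therefore cannot be predicted or corrected afterwards.

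Because *completed* is undefined, its meaning could also be settled once outcomes are known. Deaths among non-completers would still appear in the safety data, while the mortality comparison used a selected denominator. Section 7.2 intends conclusions on physiology, ventilation duration and survival, and use of the data to plan larger studies, so a distorted estimate would carry forward.

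**Working it through.** The plan has no figure to reproduce: 7.2 says a power calculation could not be done.

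**Step 1. What *completed* could mean.** Section 5.1 equates the end of the study with 72 hours, when the device comes out. Section 6.2.3 says "clinical status and outcome will be reviewed 30 days after study completion", which also puts completion at the end of treatment. Section 4.4 points elsewhere: "Participants will be involved for approximately 30 days, including screening, treatment, and follow-up".

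| Reading | Withdrawn or discontinued before that point | Deaths before that point |
|---|---|---|
| 72 hours | excluded | not stated; possibly excluded |
| about day 30 | excluded | not stated; if excluded, mortality is 0% in both arms by construction, the least plausible reading |

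No section says that a death is a non-completion. Excluding withdrawn and discontinued patients needs only the ordinary meaning of the word.

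**Step 2. Bias in P/F.** From the documents: 11 per arm (3.1). Assumed: no true effect; normal P/F values in SD units; a fraction p of the warming arm lost, namely those lowest on a propensity with correlation ρ to P/F. The expected shift in the warming mean is

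bias = ρ · φ(z_p) / (1 − p),

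where φ is the standard normal density and z_p its p-quantile. The standard error of the difference without loss is √(2/11) = 0.426 SD.

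For p = 0.20 and ρ = 1: 0.280/0.80 = 0.350 SD.

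| ρ | p = 10% | p = 20% | p = 30% |
|---|---|---|---|
| 1 (worst case) | 0.195 | 0.350 | 0.497 |
| 0.5 | 0.097 | 0.175 | 0.248 |
| 0.3 | 0.058 | 0.105 | 0.149 |
| 0 | 0 | 0 | 0 |

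A direct simulation agrees in size: dropping the worst 1, 2 or 3 of 11 in one arm shifts its mean by 0.16, 0.30 or 0.42 SD.

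**Step 3. False positives for warming.** 40,000 simulated trials per scenario, pooled t-test, nominal 2.5% per side (assumed, since the plan states no alpha), loss in the warming arm only:

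| ρ | p = 10% | p = 20% | p = 30% |
|---|---|---|---|
| 1 (worst case) | 6.1% | 11.1% | 17.3% |
| 0.5 | 4.0% | 5.6% | 7.0% |
| 0.3 | 3.4% | 4.1% | 4.8% |
| 0 | 2.6% | 2.4% | 2.5% |

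Other patterns:

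- Loss of 30% (warming) against 10% (control): bias 0.15 SD and 4.9% at ρ = 0.5; 0.30 SD and 10.8% at ρ = 1.
- Equal loss of 20% in both arms: no bias, about 2.5%.
- Best warming patients lost instead (20%, ρ = 0.5): bias −0.17 SD, with 5.5% false positives *against* warming.

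A repeat run gave the same results within simulation error.

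**Step 4. Mortality.** Assumed: 4/11 deaths (36.4%) in each arm, so the true difference is 0.

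- Two warming patients who die are removed: 2/9 = 22.2%; 22.2 − 36.4 = −14.1 points before rounding, a spurious benefit.
- Two warming survivors are removed: 4/9 = 44.4%; 44.4 − 36.4 = +8.1 points before rounding, a spurious harm.

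Starting from 5/11 the pattern holds: 3/9 − 5/11 = −12.1 points, and 5/9 − 5/11 = +10.1 points.

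**The case against.** **The wording is not explicit.** Section 7.4 says who will be included; it does not say *only*, does not say *efficacy*, and names no excluded group. That is true, but completion as a third joint condition has no function unless it excludes someone. Reading it as an efficacy rule is fair because 7.3.2 handles safety separately.

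**Early deaths.** Mortality is a named endpoint, so a recorded death has supplied its data, and a P/F value after death is missing under any analysis set. Both points stand. Early deaths are therefore only a possible exclusion, and the P/F analysis needs its own rule for death.

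**Routes to loss are narrow.** The intervention lasts 72 hours in ventilated patients, much of the data comes from chart review, and 6.3 sends a patient with persistent device malfunction to standard care without calling that withdrawal. Few patients may be lost. But with 11 per arm, one or two are enough to move the estimate.

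**The size is assumed, and the headline rates are one-sided.** Errors in the other direction fall as those for warming rise. With loss in the warming arm only, total two-sided error at ρ = 0.5 is about 5.5%, 6.5% and 7.9% for 10%, 20% and 30% loss, against 5%; at ρ = 0.3 it is about 5.2%, 5.4% and 6.0%. The Fisher p-value for 2/9 against 4/11 is about 0.64, so chance variation exceeds the illustrated shift. This is correct and limits any claim about significance testing. It does not remove the bias in the estimate, which is what a pilot passes on.

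**It is a pilot.** Section 7.3 still specifies between-group tests and 7.2 still intends conclusions from them.

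**Conclusion.** The concern holds. Followed as written, the plan conditions every efficacy comparison on an undefined event after randomisation that unblinded staff can influence. This must be fixed before analysis.

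Confidence is high that withdrawn and discontinued patients would be excluded, and lower for early deaths, where the text is silent. The direction of bias is not fixed. For P/F, moderately informative loss confined to the warming arm (ρ = 0.5, 10% to 30%) gives a bias of 0.10 to 0.25 SD against a standard error of 0.43 SD. The worst case gives 0.20 to 0.50 SD. Loss that is equal or unrelated to outcome gives none. The mortality examples shift the difference by 8 to 14 points. All of this rests on assumed loss, correlation and death rates.

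**What to change.** Replace 7.4 with a statement that all randomised patients are analysed in the arm assigned, whether or not they received, tolerated or completed the intervention, using all data obtainable under the consent and authorisation rules in 6.5.1 and 9.1. In addition:

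- Use all randomised patients as the mortality denominator, and report any with unknown vital status by arm.
- Define *completed*, and keep completers as a labelled sensitivity analysis.
- State in advance how death and extubation before 72 hours enter the P/F comparison. One option is worst rank for death and best rank for liberation alive, compared with the Mann–Whitney test already named in 7.3.
- It would also help to say in 6.5 that stopping the device does not by itself end data collection.

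The cost is one or two paragraphs of wording and no extra patients; the core change adds no procedures. If data collection continues after the device is stopped, later viral-load samples may count as study procedures and need consent. Some outcomes of withdrawn patients will stay unavailable, because 6.5.1 needs permission and names only survival status, and 9.1 limits new data once authorisation is revoked. The rank option turns P/F into a composite that is harder to read in mmHg.

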6.3 Rescue Therapy

The core warming device will be removed and replaced if at any time there is evidence of a potential device malfunction. The device can be easily removed and replaced during treatment if needed. Should evidence of continued malfunction occur after replacement of the study device, the device will be removed, allowing the patient to undergo the standard of care with respect to temperature monitoring and control.

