8.5 Expedited Reporting of Events

Any study-related unanticipated problem posing risk to subjects or others, and any type of unanticipated serious adverse event or unanticipated adverse device effect, will be reported to the IRB in accordance with the institutional and FDA requirements. Investigators will use the appropriate SAE/UP CRF to record events and a line item will also be added to the AE log CRF.

The minimum necessary information to be provided at the time of the initial expedited event report includes:

• Study identifier• Study Center• Subject number• A description of the event• Date of onset	
• Current status• Whether study intervention was discontinued• The reason why the event is classified as serious• Investigator assessment of the association between the event and study intervention
---	--

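### Section 7.4 analyses only randomized patients who complete the study, with completion undefined, so a patient discontinued for an adverse event can drop out of the efficacy and mortality comparisons

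*Combined protocol and SAP*

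**What the plan says.** The analysis population is a single sentence in Section 7.4: "All patients enrolled, randomized to a study arm, and completed in the study will be included for analysis". The three conditions are cumulative, so randomization alone does not qualify a patient. Section 7.3.1 (Efficacy Analysis) names no population. Section 7.3.2 covers everyone randomized, but only for adverse event data.

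No section defines completion, and usage differs:

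- Section 5.1 equates completion of the study with the end of 72 hours of device use. Section 6.2.3 agrees: "Participant's clinical status and outcome will be reviewed 30 days after study completion".
- Section 6.5 states "It will be documented whether or not each subject completes the clinical study" and, in the same section, counts withdrawals up to the 30-day visit.

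On early stopping, Section 6.5 says of subjects: "They may also be discontinued from the study at the discretion of the Investigator". The grounds include adverse events, clinical necessity and safety. Section 8.5 lists "Whether study intervention was discontinued" among the items of an expedited report, which is not a follow-up rule. Only for repeated device malfunction does the plan say what happens next: "the device will be removed, allowing the patient to undergo the standard of care" (Section 6.3).

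The primary endpoint paragraph of Section 7 adds: "This endpoint will be compared between patients receiving core warming and those randomized to undergo standard care".

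**The concern.** If a patient's presence in the analysis depends on how the patient fared after randomization, the two groups are no longer the groups that were randomized. Take a warmed patient who has a new stroke or cardiac arrest. The investigator may stop warming and discontinue the patient from the study under Section 6.5, and Section 7.4 then leaves that patient out of all three comparisons. Physicians and the study team know the allocation (Sections 5.2 and 8.6), so both the discontinuation and the later reading of completion are made with the arm known.

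Sections 6.5 and 7.4 apply to both arms, and an early death could be read as non-completion in either. The warming arm has one extra reason for stopping, namely the device and its effects, so exclusion could favour warming. That direction is plausible, not certain. Recruitment ends at 22 randomized (Section 4.5), so excluded patients are not replaced. Section 7.2 intends the data for planning larger studies, which would inherit a selected estimate.

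**Working it through.** The plan states no power, variance or dropout figure, so there is nothing of its own to reproduce beyond 11 + 11 = 22. The check has a textual part and an illustrative part.

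**Text.** Two readings of completion are possible.

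1. *Followed to day 30.* Read strictly, every death would be a non-completion and the mortality endpoint would be empty, so this reading is hard to sustain.
2. *72 hours of assigned management.* This fits Sections 5.1 and 6.2.3. Patients who die or withdraw after 72 hours are kept; patients discontinued from the study before 72 hours are not. A death before 72 hours is left unclear.

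Under either reading, early discontinuation for an adverse event takes the patient out.

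**Mortality.** Inputs: 11 per arm (Section 3.1); x deaths in each arm, with x from 3 to 6 (assumption), so the true difference is zero. Remove k warmed patients who died:

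- Warming-arm mortality becomes (x − k)/(11 − k).
- Standard error (SE) of the difference = √(2p(1 − p)/11), with p = x/11.

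| x | p | SE (points) | k = 1 | Shift (points; SE) | k = 2 | Shift (points; SE) |
|---|---|---|---|---|---|---|
| 3 | 27.3% | 19.0 | 2/10 = 20.0% | −7.3; 0.38 | 1/9 = 11.1% | −16.2; 0.85 |
| 4 | 36.4% | 20.5 | 3/10 = 30.0% | −6.4; 0.31 | 2/9 = 22.2% | −14.1; 0.69 |
| 5 | 45.5% | 21.2 | 4/10 = 40.0% | −5.5; 0.26 | 3/9 = 33.3% | −12.1; 0.57 |
| 6 | 54.5% | 21.2 | 5/10 = 50.0% | −4.5; 0.21 | 4/9 = 44.4% | −10.1; 0.48 |

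Removing one death from each arm gives (x − 1)/10 − (x − 1)/10 = 0. Removing one from control only gives the same shift against warming. With k = 2 the warming arm has 9 patients, below the 10 per group named in Section 7.2.

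**P/F ratio.** Suppose the excluded patient's change is D worse than the mean M of the other ten. The mean of all eleven is M − D/11, so exclusion raises the arm mean by D/11.

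- D = 50 to 100 mmHg (assumption): 50/11 = 4.5 and 100/11 = 9.1 mmHg.
- SE of the difference = SD × √(2/11). With an SD of change of 60 to 100 mmHg (assumption): 25.6 to 42.6 mmHg.
- Ratio: from 4.5/42.6 = 0.11 to 9.1/25.6 = 0.36 SE.

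As a check that needs no mmHg values, simulating 11 normal changes and dropping the worst one moves the arm mean by about 0.16 SD. Since √(2/11) = 0.426, that is 0.159/0.426 = 0.37 SE, close to the upper end above.

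**The case against.** The strongest points on the other side are these.

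- *Survival is sought for withdrawn patients.* Section 6.5.1 asks their permission to look up survival, and Section 9.1 seeks at least vital status after authorization is revoked. Sections 7.3.2 and 8.2 should also capture adverse events, including deaths, to day 30. So the death record is not what is at risk. But the look-up needs permission, and no text puts its result into the mortality comparison.
- *The 72-hour reading is the sensible one, and it shrinks the exposure.* This stands: later deaths and withdrawals would be included. Early discontinuation is still excluded.
- *Foreseeable device problems already have rules.* At 39.8°C the device setting is lowered (Section 3.1.2), and malfunction leads to replacement or standard care (Section 6.3). This also stands. What remains is discretionary discontinuation under Section 6.5, which is permitted and not required. No text says that warming must stop after a stroke or arrest.
- *The contrast in Section 7 between receiving and being randomized may be loose drafting.* Agreed; Section 3.1 defines both groups by randomization. The concern does not depend on it.
- *Analysing everyone does not create missing P/F values.* Correct. Blood gases are recorded only if routinely taken, a patient who has died has no later value, and patients extubated early, who are doing well, may also lack one. The fix fully serves mortality and ventilation duration, and P/F only where measured.
- *It is an unpowered pilot and the effect is small.* For one exclusion, yes. Sampling error, however, is visible in the reported interval, and this bias is not.

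**Conclusion.** The concern holds. The only efficacy population in the plan is conditional on an undefined completion, and Section 6.5 allows discontinuation from the study on grounds related to outcome, so the rule as written permits outcome-dependent exclusion. Exclusion is possible, not certain, and its direction is uncertain.

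The size rests on assumed event counts and assumed P/F spread. One excluded warmed death shifts mortality by 0.21 to 0.38 SE, and one excluded poor P/F response shifts that mean by 0.11 to 0.36 SE: small for a trial of this size. Two excluded deaths shift mortality by 0.48 to 0.85 SE, which is no longer negligible. No probability is attached to either case, because the documents give no discontinuation rate. The change is worth making because it costs almost nothing and the estimates are meant to inform later trials.

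**What to change.** - **Section 7.4:** analyse all randomized patients in the arm to which they were assigned, whether or not warming was completed. Define completion as 72 hours of assigned management, and use it only for a supportive analysis.
- **Section 7, primary endpoint:** describe the warming group as those randomized to core warming, not those receiving it.
- **Section 6.5:** separate stopping the device from withdrawal from the study. A patient whose warming is stopped stays in, with the 24, 48 and 72 hour measurements where available and the 30-day chart review, unless consent is withdrawn.

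The cost is wording in three places. No patients or visits are added: P/F comes from routine blood gases, and the 30-day outcomes can be taken by chart review (Section 4.4). The statistical price is dilution. A warmed patient who gets none of the effect reduces the estimated effect by at most about 1/11, or 9%.
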